STUDY PROTOCOL WITH STATISTICAL ANALYSIS PLAN

Official title:

Physical Therapist as Primary Assessor for Patients With Knee Pain in Primary Care

NCT number: NCT03715764

The Regional Ethical Review Board in Gothenburg approved the study 2013-03-15, reference numbers: 979–12, T674–13, T497–14, T791–15.

Document date: Protocol published and released on clinicaltrial.gov 2018-10-22.

Study Description

Brief Summary:

In order to manage the future increase in osteoarthritis consultation, patients with osteoarthritis could be assessed by a physical therapist first, so that other patients with more severe conditions could get faster access to a primary care physician. In Swedish primary care, physicians and physical therapists are primary assessors for patients with suspected knee osteoarthritis. However, it is unclear if there are any differences between these managements in improving health-related quality of life (HrQoL), pain, physical function and self-efficacy.

There is a limited amount of studies about the impact on HrQoL, pain intensity, self-efficacy and physical performance in patients with knee pain being assessed and evaluated by a physical therapist as a primary assessor.

The overall purpose of this study is to evaluate the effects on self-rated HrQoL, pain intensity, self-efficacy and physical performance with either a physical therapist or a physician as primary assessor for patients with knee pain within primary health care.

Problem statements

Which effect does a clinical pathway with a physical therapist as primary assessor for patients with knee pain...

... have on self-rated HrQoL compared with a physician as primary assessor?

... have on self-rated pain intensity compared with a physician as primary assessor?

... have on physical performance compared with a physician as primary assessor?

... have on self-efficacy compared with a physician as primary assessor?

It is expected that this study will show the effects of two different primary assessors for patients with knee pain consulting primary health care. The results could clarify which profession that is most appropriate to be the primary assessor for patients with knee pain in primary health care.

Detailed Description:

Patient Recruitment Recruiters: Primary care centers.

Screening procedure

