Nurses at the primary care centers will get information about the study and the screening protocol from the data collector and project leader. There will be contact persons at each recruiting unit that will be responsible for the protocols and to contact the data collector when a patient fulfills all the criteria for participation. The project leader will have regular contact with the contact persons at the recruiting units. All screening protocols will be sent to the data collector. All participants will get orally and written information about the study from the data collector, and patients will provide written informed consent.

Randomization

Using a computer-generated list of random numbers, participants will be randomly assigned to being assessed, diagnosed and treated either by a physiotherapist or a physician first. A project coordinator is included among the health care providers in the study, but will not be involved in the screening procedure nor the data collection. The project coordinator will manage the sequence generation, allocation concealment, enrolment and assignments of participants and keep the concealed randomization scheme and sequentially numbered, sealed envelopes in a locked cupboard (in the same building where the enrolment will be), only available for the project coordinator. The project coordinator reveals the allocation to the participant shortly after the baseline measurement and to the health care providers.

Participants and health care providers in both groups will be aware of the allocated group, whereas data collector, data analyst and statistician will be kept blinded of allocation until completion of all outcome assessments.

The blinded data collector and analyst (is a physical therapist) whom is not involved in assessing diagnosing and treating patients with knee osteoarthritis while the study is conducted.

Data Collection

Measurements will be collected at baseline (before randomization), at 3-, 6-, and at 12 months follow up. All data will be coded and managed according to the Data Protection Act (1998:204), which means that all data will be confidential, and no unauthorized will have access to the patient registry. The results will be presented at group level; therefore, no individual information can be identified. Data will be saved for at least 10 years to enable audit.

Sample size

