To detect a minimal clinical improvement in health-related quality of life of 0.121(SD 0.2) on the EQ5D-index, with a two-sided 5% significance level and a power of 80%, a sample size of 50 patients per group will be necessary, given an anticipated dropout rate of 14%.

Statistical analysis

Data will be analyzed descriptively and presented as numbers and percent, mean and standard deviation or median and 25th to 75th percentiles. The primary outcome will be mean change in HrQoL (EQ5D-index and EQ5D-scale) and secondary outcomes will include mean change in pain intensity (VAS), physical performance (30CST) and self-efficacy (ASES-S). The changes in scores for the outcomes will be constructed by calculating raw differences between baseline and the follow ups.

For group comparison the X²-test will be used for nominal data and Fischer's exact test for small numbers, parametric student t-test for continuous variables and Mann-Whitney's test for ordinal data and at skewed distributions. Statistical analysis will be made in SPSS Windows and the analysis will be applied with intention-to-treat (ITT). The level of significance will be p< 0.05.

Study Design

Study Type: Interventional (Clinical Trial)

Actual Enrollment: 69 participants. Anticipated enrollment, 100 participants.

Allocation: Randomized

Intervention Model: Crossover Assignment

Masking: Double (Investigator, Outcomes Assessor)

Primary Purpose: Treatment

Arms and Interventions

Intervention: Physical therapy assessment

Patients allocated to the intervention group will be assigned to an assessment and evaluation by a physical therapist. If they are diagnosed with knee osteoarthritis they will get an offer to participate in a patient education program and physical training with an individualized exercise program made by a physical therapist. Patients will be offered individual treatment if they decline to participate in the education program, or if they have another diagnosis than osteoarthritis. Anytime after the first assessment by the physical therapist, the patient will be able to contact a physician if they want to.

Control: Physician assessment

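### First assessors are nested in arm, but the tests and sample size treat patients as independent; if outcomes vary by assessor, intervals and p-values are too small for a conclusion about professions.

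*Combined protocol and SAP*

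**What the plan says.** All references are to the combined protocol and SAP.

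- **Randomization:** "participants will be randomly assigned to being assessed, diagnosed and treated either by a physiotherapist or a physician first". The patient is the unit of randomisation; the profession of the first assessor is the randomised factor.
- **Statistical analysis:** continuous and ordinal outcomes are compared by "parametric student t-test for continuous variables and Mann-Whitney's test for ordinal data and at skewed distributions", under intention-to-treat. No provider or centre term appears.
- **Sample size:** "To detect a minimal clinical improvement in health-related quality of life of 0.121(SD 0.2) on the EQ5D-index", at a two-sided 5% level with 80% power and 14% dropout, "a sample size of 50 patients per group will be necessary". No ICC or design effect is mentioned.
- **Brief Summary:** the results are meant to help clarify "which profession that is most appropriate to be the primary assessor".
- **Screening procedure:** "There will be contact persons at each recruiting unit", so recruitment runs through more than one centre.
- **Arms and Interventions:** in the control arm the attending physician decides on further measures. In the intervention arm a physical therapist designs the individual exercise programme. In either arm the patient may contact the other profession after the first assessment.

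The documents do not say how many physical therapists and physicians take part, how many patients each sees, or how a patient is directed to a particular provider.

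**The concern.** Randomising patients balances patients between arms, but it cannot balance first assessors, because by design no first assessor serves both arms. The protocol leaves room for clinicians to differ: physicians choose further measures, and physical therapists individualise the exercise programme. If some obtain better results than others, outcomes of patients who share an assessor are correlated, and the difference between arm means contains the difference between two samples of clinicians. An ordinary t-test or Mann-Whitney test leaves that component out of its standard error.

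This matters because of the intended conclusion. A statement about professions generalises beyond the clinicians who took part, so variation between clinicians belongs in the standard error. Without it, a nominally significant result could reflect a few strong or weak clinicians and still be reported as a difference between professions.

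**Working it through.** **Inputs from the documents.** Difference 0.121, SD 0.2 (standardised 0.121/0.2 = 0.605), two-sided 5%, power 80%, dropout 14%, 50 per group planned, 69 actually enrolled.

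**Assumptions, not in the documents.** Providers per arm k = 4 to 10; provider ICC 0.02 to 0.05; equal caseloads.

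**Step 1: reproduce the plan's figure.** n = 2 × (1.96 + 0.84)² × (0.2/0.121)² = 42.9 with unrounded quantiles, so 43 evaluable per arm. Then 43/0.86 = 50. The stated 50 reproduces exactly under independence, so it contains no allowance for clustering.

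**Step 2: evaluable patients at actual enrolment.** 69/2 × 0.86 = 29.7, about 30 per arm.

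**Step 3: clustering formulas.**
- Patients per provider: m = n/k
- Design effect: DE = 1 + (m − 1) × ICC
- Shortfall in interval width: 1 − 1/√DE
- Actual type I error: 2 × (1 − Φ(1.96/√DE))
- Power after allowing for clustering, normal approximation: Φ(0.605/√(2 × DE/n) − 1.96)

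**Step 4: results by formula.**

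| Evaluable per arm | k | ICC | DE | Interval too narrow by | Type I error | Power |
|---|---|---|---|---|---|---|
| 43 | any | 0 | 1.00 | 0% | 5.0% | 80% |
| 43 | 20 | 0.01 | 1.01 | 1% | 5.1% | 80% |
| 43 | 10 | 0.02 | 1.07 | 3% | 5.8% | 78% |
| 43 | 10 | 0.05 | 1.17 | 7% | 6.9% | 74% |
| 43 | 4 | 0.02 | 1.20 | 9% | 7.3% | 73% |
| 43 | 4 | 0.05 | 1.49 | 18% | 10.8% | 63% |
| 30 | any | 0 | 1.00 | 0% | 5.0% | 65% |
| 30 | 10 | 0.02 | 1.04 | 2% | 5.5% | 63% |
| 30 | 4 | 0.05 | 1.33 | 13% | 8.9% | 53% |

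Example, k = 4 and ICC 0.05 with 43 per arm: m = 10.75; DE = 1 + 9.75 × 0.05 = 1.49; √DE = 1.22. The correct interval is 22% wider than the planned one, which means the planned one is 1 − 1/1.22 = 18% too narrow.

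**Step 5: simulation.** The ordinary t-test was simulated with random provider effects in both arms. For k = 4 to 10 and ICC 0.02 to 0.05, type I error was about 5.6–11% at 43 per arm and about 5.3–8.7% at about 30 per arm, close to the formula.

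**Step 6: outside the assumed range.** With 2 providers per arm and ICC 0.05, at 43 per arm, DE is 2.02 and type I error about 17%. With 20 per arm and ICC 0.01 the effect is negligible, as the table shows.

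**Step 7: centre.** Nothing ties centre to arm, so a centre effect shared by both arms cancels on average. Simulating a t-test that ignores such effects (3–8 centres, centre ICC 0.05–0.20, 86 patients) gave type I error of 4.3–5.2%. Centre does not add to the problem.

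**The case against.** **Size unknown.** The documents give no provider count, caseload or ICC. This stands. A reader might infer that the planned intervals are definitely too narrow, or that only a small set of clinicians took part. The documents support neither statement: the first depends on an ICC above zero, and the second is only a plausible guess for a trial of 69 to 100 patients.

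**Individual randomisation makes the t-test valid.** It does, for the participating providers taken as fixed. The difficulty arises only when the result is carried over to professions. The Brief Summary words that aim cautiously, but it is the stated aim.

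**Nesting is not strict over 12 months.** Patients in either arm may later see the other profession, which may dilute a provider effect on 12-month change. This stands as a reason to expect a smaller ICC. It does not alter the nesting of the first assessor, which is what was randomised.

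**Further sources of clustering.** A reader might add the several recruiting centres, or the education programme as shared group delivery. Centre effects common to both arms do not inflate type I error, and the documents do not say that the programme is delivered in groups.

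**A mixed model is a weak arbiter with few providers.** Also true. In simulation the estimated provider variance was zero or below in about 30–48% of datasets, and the model then largely reverts to the t-test. If degrees of freedom fall to the provider level (4 per arm, 6 df, ICC 0.05), power at 43 per arm is about 49%. That argues for a sensitivity analysis rather than a condition that the primary result must pass.

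**Low enrolment is the larger loss of power.** At about 30 per arm, power is about 65% before any clustering. This is correct, and it is a separate matter from the validity of the standard error.

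**Conclusion.** The concern holds conditionally. First assessors are nested in arm by design, and neither the analysis nor the sample size allows for variation between them. For a conclusion about professions, the planned intervals and p-values are too small whenever the provider ICC is above zero and assessors see more than one patient each.

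Under the assumed 4 to 10 providers per arm and ICC of 0.02 to 0.05, with 43 evaluable per arm, the size is moderate: intervals 3–18% too narrow, type I error about 5.6–11% against the nominal 5%, and power about 63–78% against the planned 80%. At about 30 per arm, type I error is about 5.3–8.7%. Fewer providers or a larger ICC would make it worse; many providers or an ICC near zero would make it negligible.

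The documents do not support calling the planned test invalid outright. What needs to change is how far its result may be generalised, and the information readers need to judge that. The point is worth acting on because the remedy is cheap and bears directly on what the trial can conclude.

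**What to change.** In the Statistical analysis section:

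1. Keep the patient-level comparison as the primary analysis.
2. Record a code for each patient's first assessor, and report the number of assessors and the caseload per assessor in each arm.
3. Pre-specify a sensitivity linear mixed model for 12-month change in EQ5D-index: arm fixed, first assessor random within arm, Satterthwaite or Kenward-Roger degrees of freedom. Centre may be added as an optional precision term. SPSS, the planned software, can fit this through MIXED.
4. Report both intervals. If the two analyses differ, or there are very few assessors per arm, limit the conclusion to the participating providers.

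**Cost.** One paragraph in the plan and one coded variable, or two if centre is used. Since enrolment is already reported as actual, the assessor code may have to be retrieved from visit records, and the documents do not say whether these identify the assessor. The sensitivity interval will be wider, noticeably so with few providers, where the provider variance is poorly estimated and often zero. Agreement between the two analyses is then weak reassurance, which is why the number of assessors should be reported alongside.

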Allocation to the control group will involve an assessment and evaluation made by a physician. Further measures will then be determined by attending physician and the procedures that might get included are drug prescriptions, referral to x-ray examination, referral to a physical therapist or another health care provider. Anytime after the first assessment by the physician, the patient will be able to contact a physical therapist if they want to, even though if they have not been referred by the physician.

Outcome Measures

Primary Outcome Measures

Change from health related quality of life (HrQoL) at 12 months

[Time Frame: Baseline (before randomization) to 12 months]

A Swedish version of Euroqol-5 dimensions-3 levels (EQ5D-3L) will be used to assess perceived self-rated health-related quality of life. EQ5D-index respectively EQ5D-VAS will be presented. The questionnaire contain five dimensions and results in an index ranging from -0,549 to 1 using the UK tariffs. An index of 1 indicate full health. The EQ5D-VAS is a visual analogue scale ranging from 0 to 100, where 0 is worst imaginable health state and 100 is best imaginable health state.

Secondary Outcome Measures

Change from pain intensity at 12 months

[Time Frame: Baseline (before randomization) to 12 months]

The mean pain intensity (over the past month) will be measured by a visual analogue scale (VAS) ranged from 0 which will correspond no pain and 100 the worst imagined pain.

Change from physical function at 12 months

[Time Frame: Baseline (before randomization) to 12 months]

Physical performance will be measured with 30 seconds chair stand test (30CST). Number of stands will be counted.

Change from self-efficacy at 12 months

[Time Frame: Baseline (before randomization) to 12 months]

Self-efficacy will be assessed with Arthritis Self-Efficacy Scale-Swedish version (ASES-S). Each question range from 10-100, where 10 is very insecure and 100 is very confident. The questionnaire consists three subscales in how patients are experiencing their 1) pain, 2) physical function, 3) other symptoms. Each subscale results in a mean score ranging from 10 to 100 where 10 means very insecure and 100 means very confident.

Other Outcome Measures:

Demographic data

[Time Frame: Baseline (before randomization)]

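### ITT is declared without a missing-data rule, and a baseline-adjusted repeated-measures analysis would make better use of scores already collected (minor; cheap improvement)

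*Combined protocol and SAP*

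**What the plan says.** All references are to the combined protocol and SAP.

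- **Statistical analysis:** "the analysis will be applied with intention-to-treat (ITT". Outcomes are formed by "calculating raw differences between baseline and the follow ups", and the arms are compared by "parametric student t-test for continuous variables and Mann-Whitney's test for ordinal data and at skewed distributions".
- **Primary Outcome Measures:** the time frame for EQ5D-index and EQ5D-VAS is "Baseline (before randomization) to 12 months".
- **Data Collection:** the outcomes are also measured at 3 and 6 months.
- **Sample size:** loss to follow-up appears only as an allowance, "given an anticipated dropout rate of 14" percent.
- **Study Design:** "Actual Enrollment: 69 participants. Anticipated enrollment, 100 participants".
- **Arms and Interventions:** after a first visit to the physical therapist, "the patient will be able to contact a physician if they want to". The control arm has the matching freedom to see a physical therapist.
- **Randomization:** "Participants and health care providers in both groups will be aware of the allocated group". The data collector, data analyst and statistician stay blinded until all outcome assessments are complete.

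No section defines the analysis set for patients without a 12-month value. None gives an imputation rule, a repeated-measures model or a missing-data sensitivity analysis.

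**The concern.** A raw 12-month change cannot be computed without a 12-month score. Unless a rule says otherwise, the stated two-sample test therefore runs on completers, and what a dropout reported at 3 and 6 months is not used for the primary comparison. With the rule unwritten, the analyst could choose it after seeing the results.

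Two things are at stake. The first is precision: an unadjusted change score uses the baseline inefficiently, and this trial enrolled 69 of a planned 100. The second is possible bias, if dropout relates to outcome differently in the two arms. That could happen because patients and providers know the allocation, but nothing in the documents shows that it does.

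**Working it through.** **1. The plan's own figure.** Inputs from Sample size: difference 0.121, SD 0.2, two-sided 5%, power 80%, dropout 14%.

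n per arm = 2 × (1.96 + 0.84)² × 0.2² / 0.121² ≈ 42.9, so 43. Then 43 / 0.86 = 50. The stated 50 per group reproduces. The inflation returns 43 completers per arm, so the trial was sized for an analysis of completers.

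**2. Patients affected.** Observed follow-up is not given. At the planning rate, 0.14 × 69 = 9.7, about 10 patients. For range: 0.05 × 69 = 3.5 and 0.25 × 69 = 17.3.

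**3. Precision at 69 enrolled and 14% random dropout.** Take 35 and 34 patients, leaving 30.1 and 29.24 expected completers. The multiplier is √(1/30.1 + 1/29.24) = 0.260. The documents do not say whether 0.2 is the SD at a visit or the SD of change, so both readings are shown.

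*Per-visit SD 0.2.* With ρ the baseline-to-12-month correlation, SE(raw change) = 0.2√(2(1 − ρ)) × 0.260 and SE(baseline-adjusted) = 0.2√(1 − ρ²) × 0.260. The full model adds the 3- and 6-month scores, including those of the dropouts. Assumed correlations for visit pairs 0-3, 0-6, 0-12, 3-6, 3-12, 6-12:
- low: .4 .35 .3 .5 .45 .5
- mid: .5 .45 .4 .7 .6 .7
- high: .6 .55 .5 .8 .7 .8

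| Set | SE raw / adjusted / full | Power for 0.121, raw / adjusted / full |
|---|---|---|
| low | 0.061 / 0.050 / 0.049 | 0.49 / 0.67 / 0.69 |
| mid | 0.057 / 0.048 / 0.046 | 0.55 / 0.71 / 0.73 |
| high | 0.052 / 0.045 / 0.043 | 0.63 / 0.75 / 0.79 |

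Power here is from the noncentral t.

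*SD of change 0.2.* Raw change: SE 0.0519, 0.121 / 0.0519 = 2.33, power Φ(2.33 − 1.96) ≈ 64% (63% by t). Baseline adjustment multiplies the variance by (1 + ρ)/2. For an equal correlation ρ of 0.3 to 0.7 between all visits, power is 71.5-82.4% with baseline adjustment and 72.4-82.8% with the interim scores as well.

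Under both readings most of the gain is baseline adjustment. In the table, the interim scores add about 1.5 to 3.3 points.

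**4. Bias by simulation.** No true effect, per-visit SD 0.2, 14% dropout per arm, the three correlation sets above. Entries are absolute bias in EQ5D-index units. The full-model column assumes that the dropouts' 3- and 6-month scores were observed.

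| Dropout depends on | Log-odds per SD, by arm | Raw change | Adjusted only | Full model |
|---|---|---|---|---|
| 6-month change | 1 / 1 | <0.001 | <0.001 | <0.001 |
| 6-month change | 0.5 / 1 | 0.008-0.009 | 0.004-0.007 | 0.000 |
| 6-month change | 0 / 0.5 | 0.010-0.011 | – | about 0 |
| 6-month change | 0 / 1 | 0.018-0.020 | 0.008-0.014 | ≤0.001 |
| 6-month level | 0 / 1 | 0.004-0.006 | 0.010-0.013 | about 0 |
| 12-month change (unseen) | 0 / 1 | 0.025-0.029 | 0.019 | 0.009-0.015 |
| 12-month level (unseen) | 0 / 1 | 0.012-0.018 | 0.019-0.023 | 0.018 in the low set |

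For the fourth row, 0.020 is about one sixth of 0.121. In standard errors it runs from 0.018/0.061 = 0.30 to 0.020/0.052 = 0.38. In SD units it is 0.018/0.2 = 0.09 to 0.020/0.2 = 0.10, which under the same assumptions also applies to EQ5D-VAS. At 5% to 25% dropout the raw-change bias in that row is 0.007 to 0.034. With SD 0.2 read as the SD of change, it is 0.015 to 0.020 at 14%.

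If half of the dropouts have baseline only (mid set, fourth-row mechanism), the bias is 0.021 for raw change, 0.013 for baseline adjustment and 0.007 for multiple imputation.

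**The case against.** The strongest objection is that the bias argument depends on an assumed mechanism. If one-arm dropout follows how the patient feels at 6 months rather than how much the patient has changed, the raw-change bias is only 0.004-0.006 and baseline adjustment alone raises it to 0.010-0.013. The documents give no mechanism, so neither version is privileged. This stands: it cannot be said in general that baseline adjustment reduces dropout bias. What remains is that the full model removes either bias when the interim scores were seen.

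The consequence is also small. Even 0.3 to 0.4 of a standard error raises a 5% type I error only to about 6-7%, and that needs a strong slope in one arm only. This too stands and limits the severity.

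Dropout was anticipated in the sample size, and change at each follow-up may be tested at its own visit. Both are true. Neither says what happens to a missing 12-month value or brings interim scores into the 12-month comparison.

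Finally, one sentence defining the analysis set would close the gap, and a mixed model gives up the Mann-Whitney provision for skewed data. One sentence would settle the ambiguity but would not recover the precision. Skewness can be met with a bootstrap interval and by keeping the stated tests as a sensitivity analysis.

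A reader might infer that ITT is breached. The documents do not support that. Patients may see the other profession, so ITT can well mean analysis by allocated arm, and the plan meets that reading for observed patients.

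**Conclusion.** The point holds as a minor, cheap improvement. The missing-data rule is absent, and the stated test by default omits patients without a 12-month value and leaves their interim scores out of the 12-month comparison.

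The case for change rests mainly on precision: a gain in power for 0.121 of roughly 16 to 20 points if 0.2 is the per-visit SD (0.79 − 0.63 to 0.69 − 0.49), and about 8 to 18 points if it is the SD of change (72.4 − 64.4 to 82.8 − 64.4). These figures assume 69 enrolled, 14% random dropout and correlations that the documents do not give.

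A reader might also infer that the planned result is biased. That is not shown. The bias is about zero if dropout relates to outcome equally in both arms. Where one-arm dropout follows 6-month scores, it is about 0.004 to 0.020 for raw change, depending on mechanism and slope. The full model protects against this only for dropouts whose interim scores exist.

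**What to change.** Before unblinding, state the analysis set and the missing-data method, and:

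- make the primary 12-month analysis of EQ5D-index and EQ5D-VAS a baseline-adjusted repeated-measures mixed model on the 3-, 6- and 12-month scores, by allocated group, with a bootstrap interval if the data are clearly skewed. Multiple imputation from the same scores is an equal alternative and also keeps randomised patients with no follow-up;
- keep the raw-change t-test or Mann-Whitney as a sensitivity analysis labelled complete-case;
- add a not-at-random check on multiply imputed data, shifting imputed 12-month EQ5D-index values by 0 to 0.121 in one arm and then in the other. At 14% missing, the full shift moves the estimate by 0.14 × 0.121 = 0.017.

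The cost is SAP wording and some SPSS work (MIXED or multiple imputation). If allocation has already been revealed to the analyst, the new analysis must be labelled post hoc.

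The downsides should be stated in the SAP. The model assumes missing at random. Dropouts with baseline only may be handled worse than by raw change if dropout follows the level. Dropout that depends on the unseen 12-month value is at best partly corrected.

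### The sample size is correct for 100 patients, but 69 were enrolled and 80% is still the only power stated; on the plan's own inputs (0.2 read as the SD of change, t-test) power is about 63% to 70%.

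*Combined protocol and SAP*

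**What the plan says.** The Sample size section plans to detect a difference of "0.121(SD 0.2) on the EQ5D-index" at a two-sided 5% level, with "a power of 80%, a sample size of 50 patients per group will be necessary, given an anticipated dropout rate of 14"%. The Study Design section gives "Actual Enrollment: 69 participants. Anticipated enrollment, 100 participants".

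The Statistical analysis section sets out what is analysed and how:

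- The primary outcome has two measures: "The primary outcome will be mean change in HrQoL (EQ5D-index and EQ5D-scale").
- It is analysed as a change score: "The changes in scores for the outcomes will be constructed by calculating raw differences between baseline and the follow ups".
- Continuous variables are compared by t-test, with "Mann-Whitney's test for ordinal data and at skewed distributions".
- Results are summarised as numbers and percentages, or as "mean and standard deviation or median and 25th to 75th percentiles".
- The only criterion for a finding is "The level of significance will be p< 0.05".

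The document contains no second power figure, no detectable difference or precision for 69 patients, and no commitment to a confidence interval.

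**The concern.** The trial was sized to need 86 evaluable patients and enrolled 69 in total. A reader who relies on the stated 80% would give a non-significant result more weight than the enrolled trial supports. This matters here because the Brief Summary expects the results to help decide which profession should assess knee pain first, so a null result could be taken to mean that the two pathways do equally well.

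The plan's only decision criterion is a p-value. If means, SDs and group sizes are reported, a reader can work out the interval. If skewed data lead to medians and percentiles instead, which the plan permits, a reader cannot.

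**Working it through.** **Inputs from the plan.** Difference 0.121, SD 0.2, two-sided alpha 0.05, power 80%, dropout 14%, 50 per group, 69 enrolled.

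**Assumptions.** SD 0.2 is the SD of the 12-month change, because change is what is analysed. The comparison is a t-test. The 69 were split 1:1. Actual dropout is not in the document, so 0% and 14% are both shown.

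**1. The plan's figure.** Standardised difference = 0.121 / 0.2 = 0.605. By the normal approximation, n per group = 2(1.96 + 0.8416)² / 0.605² = 42.9, so 43 per group and 86 in total. Allowing for dropout, 43 / 0.86 = 50.0. The stated 50 per group reproduces.

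**2. Evaluable patients from 69.** With no dropout, 69 / 2 = 34.5 per group. With 14%, 69 × 0.86 = 59.3, or 29.67 per group. Both are below 43.

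**3. Power, detectable difference and precision.** Power comes from the noncentral t distribution with 2n − 2 degrees of freedom and noncentrality 0.121 / (0.2 × √(2/n)). The expected 95% half-width is t(0.975, 2n − 2) × 0.2 × √(2/n).

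| Evaluable per group | Noncentrality | Power | Chance of missing 0.121 | Difference detectable at 80% | 95% half-width |
|---|---|---|---|---|---|
| 43 (planned) | 2.81 | 79.2% | 21% | about 0.12 | 0.086 |
| 34.5 (69, no dropout) | 2.51 | 69.7% | 30% | 0.137 | 0.096 |
| 29.67 (69, 14% dropout) | 2.33 | 63.0% | 37% | 0.148 | 0.104 |

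The normal approximation gives 80%, 71% and 64% in the same three rows. Intermediate dropout of 5% and 10% gives t-test power of 67% and 65%. An assumed 40/29 split gives 69% with no dropout and 62% with 14%.

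**4. Sensitivity to the SD of change (assumed values).**

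| SD of change | Power, no dropout | Power, 14% dropout |
|---|---|---|
| 0.15 | 91% | 86% |
| 0.18 | 79% | 72% |
| 0.20 | 70% | 63% |
| 0.22 | 61% | 55% |
| 0.25 | 51% | 45% |

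The largest SD of change that keeps 80% power is 0.177 with no dropout and 0.164 with 14%.

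**5. If 0.2 is the SD of a single score.** With equal SDs at both times, the SD of change is 0.2 × √(2(1 − r)), where r is the correlation between baseline and 12 months. The document gives no r. Keeping 80% power needs r = 1 − (0.1768/0.2)²/2 = 0.61 with no dropout, or 1 − (0.1635/0.2)²/2 = 0.67 with 14%. An assumed r of 0.3 gives 55% and 49%; 0.5 gives the same 70% and 63% as above; 0.7 gives 89% and 84%.

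**6. Mann-Whitney.** In 20,000 simulated trials with normal data and SD 0.2, power was 78% at 43/43, 67% at 35/34 and 60% at 30/29. The shortfall is similar, but this does not cover skewed data, the situation in which the plan would use that test.

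**The case against.** The strongest reply is that nothing is false or hidden. The sample-size text is a forward-looking statement, it is correct, and the actual enrolment is printed openly in the same document. Nowhere does the plan claim that 69 patients give 80% power. Enrolment is recorded as actual, so no design decision turns on a new power figure, and once results exist the estimate and its interval say more than any recalculated power. All of that is fair. It is why this is a point about missing text and not an error in the calculation, and why the interval is the more useful half of the remedy. It does not remove the gap, because no interval is promised and 80% is the only figure a reader has.

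A second reply is that the 63% to 70% range is conditional. This stands. The sample-size calculation uses only the ratio 0.121/0.2 and cannot show which SD was meant. If 0.2 is the SD of a single score and the correlation is high, 80% power could survive. Nor is 63% a floor, since 14% is only the planned dropout. The conditions therefore belong beside any power figure that is quoted.

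A third reply is that the planned trial would already have had a wide interval: 0.086 is 71% of 0.121, and 0.096 to 0.104 is 79% to 86%. The added width is thus about 12% to 21%, which is a moderate loss. Finally, the outcome is defined as a mean change, so the case where only medians are reported may never arise.

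Recalculating power here is not the discredited practice of computing it from observed results. Only planning inputs and the known enrolment are used.

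**Conclusion.** The concern holds, as a point that should be fixed. The original calculation is sound; its consequence at the recorded enrolment is not stated. On the planning inputs, no dropout rate from 0% to 14% gives 80% power with 69 patients. The loss is roughly 9 to 16 percentage points against the 79% obtained by the same t-test method at the planned size, and the expected half-width comes close to the difference the trial was sized to find. The conclusion rests on 0.2 being the SD of the 12-month change, on a t-test and on a near-equal split. The first of these matters most, and the sponsor can settle it. The figures apply to the EQ5D-index only; EQ5D-VAS, the other primary measure, has no power calculation at all.

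**What to change.** Enrolment is recorded as actual, so change the text and do not recruit more patients.

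1. Add beside the sample-size paragraph: *69 of the planned 100 patients were enrolled. On the planning inputs (EQ5D-index difference 0.121, SD 0.2 taken as the SD of the 12-month change, two-sided 5% t-test, 1:1 split), power is about 70% with no dropout and 63% with 14%, against 79% by the same method at the planned 43 evaluable per group. The difference detectable with 80% power is about 0.14 to 0.15. Power is higher if the SD of change is below 0.2 and lower if it is above. The figures are approximate if Mann-Whitney is used.*
2. State whether SD 0.2 describes the score or its change, and adjust that wording if it is the score.
3. Commit to reporting the between-group difference in 12-month EQ5D-index change with its 95% confidence interval, even if Mann-Whitney supplies the p-value, and discuss the interval against 0.121.
4. Report a 95% confidence interval for EQ5D-VAS in the same way.

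Do not add an equivalence rule at ±0.121, since the plan set no such margin.

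The cost is one paragraph and two intervals. The data, tests and outcomes stay as they are. The drawback is that the stated power becomes less favourable.
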